Objectives	Evaluate whether a treatment plan based on CT angiography can accurately and precisely identify the target nidus as compared to standard cerebral arteriography fused to MRI.
Number of Subjects	14
Diagnosis and Main Inclusion Criteria	Patients with AVM requiring SRS, age \geq 10 years. Size $\leq 3.5\text{cm}$; $\leq 12\text{cc}$
Study Product(s), Dose, Route, Regimen	Radiation, Stereotactic Radiosurgery with Gamma Knife, using standard of care, as directed by the treating Radiation Oncologist and Neurosurgeon.
Duration of administration	One day procedure
Reference therapy	Radiation, Stereotactic Radiosurgery of AVM using standard of care approach and MRI
Statistical Methodology	The target volume generated by IR angiogram will be compared to the target volume generated by CT angiogram using the Sorensen-Dice coefficient and surface to surface distance.

1.0 BACKGROUND AND RATIONALE

1.1 Disease Background

Arteriovenous malformation (AVM) is a congenital vascular malformation where there is direct arterial to venous connections without an intervening capillary network, creating a system of feeding arteries, tangled malformation or nidus, and draining veins engorged from the high pressure (Figure 1). Acting as a shunt, AVM results in a high pressure arteriovenous communication. The average annual risk of bleeding is 2–3 %¹. Abnormal flow and a vascular “steal” phenomenon appear to be associated with larger AVMs and have been suggested to underlie some clinical symptoms associated with cerebral AVMs².

[figure not shown]

Figure 1: Feeding artery, nidus and draining vein of AVM

A combination of MRI and interventional cerebral arteriography is often used to assess the likely success and risks of surgical, endovascular, or stereotactic radiosurgery (SRS). Surgical resection remains the primary treatment modality for patients with AVM as it eliminates the source of hemorrhage. However, surgery may be intolerable in cases with AVM in deep locations and / or eloquent areas of the brain. Embolization may be used as an independent curative therapy, however, it is more commonly utilized prior to surgery as an adjunct (reviewed in ³). SRS is another local treatment modality that has been established as an effective treatment for cerebral AVM⁴. Although commonly used, CT angiography for the treatment planning of SRS for AVM has not been validated against formal cerebral arteriography.

1.2 Stereotactic Radiosurgery (SRS)

SRS is an effective and minimally invasive approach compared to surgery. Its main drawback is the longer duration of time to achieve total obliteration of the AVM, ranging from six months to five years after the procedure⁵. Although the effect of SRS is not immediate, SRS is a preferable treatment option for patients with AVMs that are not surgically accessible or in patients with comorbidities that make them poor surgical candidates. In SRS, a potent dose of highly conformal radiation is delivered in a single fraction to the target nidus, leading to elimination in blood flow through the nidus in 40-80% of patients depending on AVM size⁶. SRS of AVM leads to the closure of the malformed vascular lumen, likely due to endothelial cell proliferation and fibrosis. In many centers that perform SRS, patients with AVM only undergo T1-weighted MRI image with gadolinium contrast to delineate the target volume. While MRI provide excellent soft tissue information, the AVM nidus is often difficult to be distinguished from the draining vein or a hematoma in the case of a previous hemorrhage, which leads to a treatment target considerably larger than the nidus itself. Other centers use volumetric CT angiograms to define the target.

At our institution, we routinely perform interventional cerebral arteriography on the day of the SRS procedure for improved target delineation. Following image acquisition, an neurointerventional specialist manually delineates the AVM nidus on the planar angiogram images; these images are stereotactically fused with the MR images. The nidus of the AVM is then contoured by the Neurosurgeon using the mutual information, to distinguish the AVM from a draining vein or the surrounding hematoma if there was prior hemorrhage. This extra information from the angiography allows the target volume to be significantly smaller compared to targets generated solely from MRI sequence, allowing us to spare the surrounding normal brain parenchyma. Even though the addition of angiography is time consuming and requires multi-modality team care, this approach has allowed our institution to treat the smallest possible target, yet achieve excellent obliteration rates of AVM with very low toxicity from the procedure. At our institution we also use CT angiogram at the treatment team's discretion to further enhance the accurate delineation of the final treatment

target volume. However, it had not been routinely done due to uncertain benefit in treatment planning and a concern for renal burden from additional intravenous (IV) contrast usage.

1.3 Rationale for the Protocol

While interventional cerebral arteriography is the gold standard for the diagnosis, treatment planning and follow up of AVM, it is an invasive procedure that comes with the risk of stroke (< 1 %), arterial dissection (< 0.5%), transient ischemia (< 3 %) and bleeding at the puncture site⁷⁻¹¹. The risk of developing neurologic complications after the procedure appears to be elevated in patients with atherosclerotic cerebrovascular disease or cardiovascular disease, patients older than 55 years of age, and with fluoroscopic time beyond 10 minutes^{11,12}. Interventional cerebral arteriography is also the gold standard in the diagnosis of acute ischemic stroke. Nevertheless, it is rarely performed nowadays as the primary diagnostic test in the acute setting. The main reason for the change in practice pattern is the advent of the noninvasive techniques such as CT and MR angiography and duplex and transcranial Doppler ultrasound that can rapidly visualize intracranial arterial disease. While SRS of AVM is not performed in the acute setting, performing a noninvasive angiogram instead of interventional arteriography will reduce the total treatment time by three to four hours. Such reduction in the procedure time will likely improve patient comfort and satisfaction as it will reduce the time these patient would need to wear the uncomfortable stereotactic headframe.

While noninvasive imaging with CT and MR angiography have still not replaced interventional cerebral arteriography, technical advances are allowing these modalities to serve as powerful adjuncts (reviewed in ¹³). In fact,

interventional cerebral arteriography only provides two-dimensional (2D) spatial information when combined with the gamma knife treatment planning system and requires an MRI of the brain for the 3D information (Figure 2) while CT or MR angiography provide 3D information that could be used in the treatment planning of SRS. However, the use of these reconstructed angiographic images for treatment planning of SRS has not been validated against interventional cerebral arteriography.

Major risk factor for contrast agent-induced nephropathy is underlying renal dysfunction¹⁴. If a patient's renal function

[figure not shown]

Figure 2: (A) Postcontrast T1 weighted MRI with a depiction of AVM target without interventional cerebral arteriography (B) Anterior-posterior (AP) and (C) right-left (RL) fluoroscopic images from cerebral arteriography used for nidus identification. X and + marks of the stereotactic frame depicted on these images enable fusion with MRI. (D) Fused MRI showing 2D nidus location from (B) and (C) projected as blue lines to delineate the nidus as target (pink outline).

is truly normal, then a high volume of contrast will not lead to nephropathy. In practice, however, the dose of contrast is a concern in patients undergoing catheter angiography and CT on the same day because certain doses are associated with adverse contrast reactions and nephropathy, although the data on this issue are limited¹⁵. Iopamidol (ISOVUE®) is the main intravascular contrast agent used at our institution. For multiple procedures on same day, the maximum recommended dose is 225 mL of ISOVUE-370 for adults and 125 mL for children between the ages of 10 to 18 (ISOVUE package insert, Bracco Diagnostic Inc, Cranbury, NJ). In these circumstances, due regard should be given to the clinical need for an optimal study with an adherence to the maximum recommended dose. In the vast majority of cases, contrast agent-induced nephropathy will be manifest by a transient increase in serum creatinine level, which usually peaks at 4–7 days and gradually returns to baseline¹⁴. A persistent elevation of serum creatinine level is unusual. Typically, both CTA and conventional angiography can be performed with less than 100cc of IV or IA contrast administration.

Finally, interventional cerebral arteriography adds an extra few hours to the overall clinic stay with an extra hour for the actual procedure, use of interventional radiology and recovery facility, and requires the patient to lay flat for several hours after the procedure due to the access of femoral artery. CT angiogram is expected to increase the procedure duration by another 15-30 minutes for transfer, set up and image acquisition. Although the patients enrolled on this study will endure approximately 30 minutes longer stay at the clinic, replacing the interventional cerebral arteriography with CT angiography in the treatment planning of SRS may ultimately reduce the total hospital stay by approximately three hours.

In summary, we propose to evaluate whether a target volume based on CT angiography can serve as a reliable substitute for a target based on interventional cerebral arteriography. Patients on this protocol will still get treated based on target generated by interventional cerebral arteriography but also receive CT angiography. If the target volume based on CT angiography are adequate compared to their invasive counterpart, future investigators may selectively omit performing interventional cerebral arteriography in the treatment planning for SRS of AVM. Use of CT angiography may lead to reduction in the risk from the procedure and cost, improve the efficiency of the treatment process ideally without compromising the success of the procedure, with greater patient comfort and satisfaction.

2.0 STUDY OBJECTIVES

2.1 Primary Objective

To evaluate whether target(s) based on CT angiogram can accurately and precisely identify the target nidus as well as an interventional cerebral arteriogram.

2.2 Secondary Objectives

- 2.2.1** To analyze and compare dosimetric parameters, including planning target volume (PTV) and V12, of an SRS treatment plan based on MRI alone, with interventional cerebral arteriography, and CT angiograms.
- 2.2.2** To evaluate the total time it takes to perform the additional CT angiograms and compare it to the duration of the interventional procedure.

2.3 Endpoints

The primary endpoint of this study is to compare the target generated from interventional cerebral arteriography (reference) to targets generated from CT angiogram and MRI alone, to assess whether noninvasive imaging approaches are non-inferior to the UTSW standard.

3.0 PATIENT ELIGIBILITY

Eligibility waivers are not permitted. Subjects must meet all of the inclusion and exclusion criteria to be registered to the study. Study treatment may not begin until a subject is registered.

3.1 Inclusion Criteria

- 3.1.1 Documented AVM with draining vein(s).
- 3.1.2 Adequate renal function (serum Creatinine < 1.5 mg/dl within 30 days of SRS) to undergo contrast CT and interventional cerebral arteriography on the same day, as determined by treating physicians.
- 3.1.3 AVM must be physically separated from the optic pathway, brainstem or spinal cord.
- 3.1.4 The maximum diameter of AVM nidus must be less than 3.5 cm and/or less than 12 cc.
- 3.1.5 Age \geq 10 years.
- 3.1.6 All men, as well as women of child-bearing potential must agree to use adequate contraception (hormonal or barrier method of birth control; abstinence) prior to study entry and for the duration of study participation. Should a woman become pregnant or suspect she is pregnant while participating in this study, she should inform her treating physician immediately
 - 3.1.6.1 A female of child-bearing potential is any woman (regardless of sexual orientation, marital status, having undergone a tubal ligation, or remaining celibate by choice) who meets the following criteria:
 - Has not undergone a hysterectomy or bilateral oophorectomy; or
 - Has not been naturally postmenopausal for at least 12 consecutive months (i.e., has had menses at any time in the preceding 12 consecutive months).
- 3.1.7 Ability to understand and the willingness to sign a written informed consent.

3.2 Exclusion Criteria

- 3.2.1 Patients without a documented AVM.
- 3.2.2 Patients with a contraindication to CT such as contrast allergy, kidney failure or implanted metal devices or foreign bodies or severe claustrophobia.
- 3.2.3 Use of Nephrotoxic drugs, such as gentamycin, high-dose nonsteroidal anti-inflammatory drugs, or certain chemotherapeutic drugs within 10 days of the procedure.
- 3.2.4 Psychiatric illness/social situations that would limit compliance with study requirements.
- 3.2.5 Patients must not be pregnant at the time of SRS treatment.

4.0 TREATMENT PLAN

This is not a therapeutic study, but rather a prospective imaging correlate study.

4.1 SRS Dose and Technique

CT angiogram and interventional cerebral arteriography will be obtained. CT angiogram may or may not be used for treatment planning as directed by the treating team. CT angiograms will be obtained in all patients to be potentially used in treatment and for protocol assessments.

4.2 Pre-therapy Assessment

Pre-therapy assessments will be performed as follows:

- Verify the patient has a documented AVM requiring radiation therapy.
- Verify age \geq 10 years.
- Verify serum creatinine is age-appropriate with adequate renal function for various contrast reagents, within 30 days of SRS.
- Verify patient is not pregnant.
- Verify women of child-bearing potential and men agree to use adequate contraception
- Verify patient is able to understand and the willingness to sign a written informed consent.
- If any of the above criteria does not meet inclusion criteria, postpone SRS as appropriate.

4.3 Toxicities and Dosing Delays/Dose Modifications

The generally accepted safe upper limit total dose of iodinated contrast in one day is 225 mL of ISOVUE-370 for adults and 125 mL for children between the ages of 10 to 18. The amount of the administered contrast may be exceeded at the knowledgeable direction of the treating radiologists. All patients enrolled on the study will be assessed for the development of toxicity according to the Time and Events table (5.3) should the subject receive more than the recommended dose of contrast. Toxicity will be assessed according to the NCI Common Toxicity Criteria for Adverse Events (CTCAE), version 5.0. Contrast related allergic reactions will also be monitored per CTCAE criteria. Only AEs reported to Radiation Oncology discipline per study calendar will be captured and assessed.

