4.6 Duration of Therapy

CT Angiogram will be obtain without exceeding the limits of IV contrast before SRS administration (SRS is not a part of this protocol), which typically be completed in one day. CT Angiogram will proceed unless:

- Subject decides to withdraw from the study, OR
- General or specific changes in the patient's condition render the subject unacceptable for further treatment in the judgment of the stereotactic team.

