5.3 Time and Events Table

	Pre-study ¹	Day 0	1 Week (-3 days, +7 days)	1 Month (+/- 10 days)
Informed Consent	X			
History and PE	X			
Serum Creatinine ²	X		X	X
Interventional Cerebral Arteriography		X		
CT Angiogram		X		
Adverse Event Assessment		X ³	X ³	X ³

1 – All screening procedures must be performed within 90 days prior to registration unless otherwise stated

2 – Within 30 days of SRS procedure

3 – Only if subject receives more than the recommended dose of contrast

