7.5 Stopping Rules

The study is designed to end if the rate of kidney injury from multiple contrast usage is higher than expected despite meeting the maximum recommended dose of contrast or an inability to consistently meet the recommended dose of contrast.

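### Sections 4.3, 4.6 and 7.1.2 do not state one rule on exceeding the contrast limit, although adverse-event assessment and the stopping rule both refer to that limit

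*Combined protocol and SAP*

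**What the plan says.** Sections 4.3 and 7.1.2 give the accepted upper limit for the day's total iodinated contrast as "225 mL of ISOVUE-370 for adults and 125 mL for children between the ages of 10 to 18". Both then allow it to be passed: "The amount of the administered contrast may be exceeded at the knowledgeable direction of the treating radiologists".

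Section 4.6 reads differently: "CT Angiogram will be obtain without exceeding the limits of IV contrast before SRS administration". It gives no exception and does not refer to 4.3. The background in 1.3 leans the same way as 4.6: "due regard should be given to the clinical need for an optimal study with an adherence to the maximum recommended dose".

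Other rules refer to the same limit:

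- In the 5.3 calendar, each adverse-event assessment (day 0, 1 week, 1 month) carries footnote 3: "Only if subject receives more than the recommended dose of contrast". Section 4.3 puts the same condition on toxicity assessment ("should the subject receive more than the recommended dose of contrast"), and 7.3.1 puts it on kidney-specific follow-up.
- Section 7.5 ends the study on either of two grounds. The first is more kidney injury than expected although the maximum recommended dose was met. The second is "an inability to consistently meet the recommended dose of contrast".
- Section 10.6 requires the study to be run as the approved protocol describes. It treats an intentional, non-emergency departure made without prior IRB approval as a major deviation.

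Serum creatinine is checked at 1 week and 1 month in every patient, whatever the contrast dose (4.5, 5.2, 5.3, 6.2).

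**The concern.** Staff on the day need to know whether the contrast limit binds absolutely or may be passed on a radiologist's decision. The sections give different answers without saying how they fit together. The answer has three consequences: whether an exceedance is a reportable departure, whether it triggers adverse-event assessment, and whether it counts towards closing the study.

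A second mismatch exists whichever answer applies. The first limb of 7.5 looks for kidney injury in patients who stayed within the limit, and footnote 3 leaves those patients without scheduled adverse-event assessment.

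**Working it through.** The point rests on setting sections side by side. No sample size, power or alpha figure enters, so the 14 patients and 92% power of section 9.2 are unaffected.

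**Step 1: scope.** Sections 4.3 and 7.1.2 concern the total iodinated contrast given in one day, so they cover arteriography and CT angiography together. Section 4.6 names the CT angiogram and speaks of IV contrast, and 1.3 itself distinguishes IV from IA administration. The only limits stated anywhere are 225 mL and 125 mL, both for the day. Section 4.6 can therefore mean that the CT angiogram must not take the day's total over the limit, that the day's total must not go over at all, or that some undefined IV portion is capped. The text does not choose. The calendar puts both procedures on day 0 and does not fix their order.

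**Step 2: a patient whose day's total passes the limit.**

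- 4.3 and 7.1.2: permitted if the treating radiologist so directs.
- 4.6: not in keeping with the section if it covers the day's total, or if the CT angiogram takes the total over. Outside the section if it covers the CT angiogram alone and a later arteriogram takes the total over.
- 10.6: a departure or not, depending on the reading of 4.6.
- 5.3 footnote 3: adverse-event assessment at day 0, 1 week and 1 month.
- 7.5: counts towards the second limb. No number defines what is consistent, and directed exceedances are not set apart from others.

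**Step 3: a patient whose day's total stays within the limit.**

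- 4.3, 4.6 and 7.1.2: all satisfied.
- 5.3 footnote 3: no scheduled adverse-event assessment.
- 7.5: any kidney injury belongs to the first limb. No expected rate is given.
- Scheduled safety data: serum creatinine at 1 week and 1 month.

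**Step 4: can the limit realistically be passed?** Section 1.3 says: "Typically, both CTA and conventional angiography can be performed with less than 100cc of IV or IA contrast administration". It does not say whether that volume is for each procedure or for both.

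- Per procedure: the sum is below 100 + 100 = 200 mL. Adults: 200 < 225, so within the limit. Ages 10 to 18: 200 > 125, so the total could pass the limit, by up to almost 200 − 125 = 75 mL.
- Combined: the sum is below 100 mL, which is under both 125 and 225.

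Patients aged 10 and over are eligible (3.1.5), so the lower limit can apply. The documents give no expected number of patients aged 10 to 18.

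**Step 5: can the rules be applied?** Footnote 3 and 7.5 both require the total volume from the two procedures. The documents do not say that it is recorded. The case report form is not among them, so it may be.

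**The case against.** The strongest reply is that the sections form a sequence. The CT angiogram is planned within the limit (4.6), a named decision-maker may exceed it (4.3, 7.1.2), an exceedance brings adverse-event assessment (5.3), and the study closes only if the limit cannot be kept consistently (7.5). Allowing single exceedances while stopping for a pattern is coherent, and it gives footnote 3 a purpose. This reading is possible, and it rules out calling the passages flatly opposed. However, no section states it. Neither 4.3 nor 4.6 mentions the other, and 7.5 does not say how directed exceedances are treated.

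The difference in scope (CT angiogram and IV contrast against the day's total) also softens the conflict. It does not remove it, because no separate IV limit exists.

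A reader might go further in three ways that the documents do not support:

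- *That following 4.6 means no patient is ever assessed for adverse events.* This needs 4.6 to cap both procedures, which it does not clearly do. An arteriogram after a compliant CT angiogram could still take the day's total over the limit.
- *That the conflict is why patients within the limit go unassessed.* The cause is footnote 3. If 4.6 were deleted, those patients would still have no scheduled assessment.
- *That the study's safety conclusion depends on the conflict.* Creatinine is unconditional, interim reports cover renal toxicity (9.3), and SAE reporting continues (7.4.1). Section 4.3 also provides for monitoring allergic reactions with no dose condition in that sentence, although its next sentence limits capture to events reported under the calendar. Safety is not among the stated objectives or the endpoint.

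**Conclusion.** The inconsistency stands as a matter of wording and scope that bears on safety conduct and compliance. The same exceedance is permitted under 4.3 and 7.1.2, arguably a departure under 4.6 and 10.6, and counted towards ending the study under 7.5. The mismatch between footnote 3 and the first limb of 7.5 is a separate defect and does not depend on how 4.6 is read.

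The practical reach depends on the meaning of the 100 cc figure in 1.3. If it is per procedure, typical volumes put only the limit for ages 10 to 18 at risk. If it is combined, typical volumes pass neither limit. The documents do not settle which is meant, and these are typical volumes rather than maxima. The sponsor should correct this. The primary comparison of targets is untouched.

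**What to change.** Reconcile 4.3, 4.6 and 7.1.2 into a single rule, used in all three places. State whether it covers the CT angiogram alone or the day's total of IV and IA contrast, and whether any exception applies. Which rule that should be is for the sponsor and the treating specialists; no view is given here.

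Then:

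- Align footnote 3 of 5.3, and the matching conditions in 4.3 and 7.3.1, with that rule.
- Align both limbs of 7.5 with it. Say which exceedances count towards the second limb, and which scheduled data serve the first limb in patients within the limit.
- Say in 1.3 whether the 100 cc figure is per procedure or combined.
- Make sure the total contrast volume from both procedures is recorded for every patient, so that footnote 3 and 7.5 can be applied.

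The cost is a wording amendment and, if the volume is not already captured, one case-report-form field. No change to sample size or analysis is needed.

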6.2 Safety/Tolerability

IV hydration will be initiated prior to all radiosurgery procedures and continued as needed until discharge. Patients will be instructed to increase hydration after the procedure and report to the treating physician in the event of developing decrease in urine output, new or worsening of swelling in extremities or around the eyes, fatigue, shortness of breath, chest pain or pressure, confusion or seizure to prevent kidney injury.

- Serum creatinine will be checked 1 week (-3 days/+7 days) after the procedure and again at 1 month (+/- 10 days) after the procedure.

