7.2 Contrast Reactions

Acute contrast reactions occur within minutes of administration of iodinated contrast. An estimated 3% of patient will experience mild contrast reaction that requires no treatment. However, moderate reactions such as bronchospasm or hypotension can occur in about 1 in 250 patients (0.4%) and about 1 in 1600 to 2500 (0.04-0.06%) of patients could experience a severe reaction²⁰. Treatment consist of administering medications directed at the specific cause of symptoms, such as bronchospasm with beta-2 agonist inhaler, while an airway or laryngeal edema should be treated with epinephrine. Antihistamine and/or corticosteroids could be administered if necessary. Delayed adverse reactions develop more than one hour after the procedure but within 7 days of IV contrast administration. It is mild in majority of cases and resolve without intervention. Non-specific symptoms range from Flu-like illness, arthralgia, aches and pains, parotitis, fever,

abdominal pain and headache. Treatment consists of antihistamine and/or corticosteroids. Severe cases may require a referral to a dermatologist.

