7.3 Adverse Event Monitoring

Adverse event data collection and reporting, which are required as part of every clinical trial, are done to ensure the safety of subjects enrolled in the studies as well as those who will enroll in future studies using similar agents. Adverse events are assessed in a routine manner at scheduled times during a trial. Additionally, certain adverse events must be reported in an expedited manner to allow for optimal monitoring of subject safety and care.

All subjects experiencing an adverse event that is reported to Radiation Oncology discipline per study calendar, regardless of its relationship to study therapy, will be monitored until:

- The adverse event resolves or the symptoms or signs that constitute the adverse event return to baseline or is stable in the opinion of the investigator;
- There is a satisfactory explanation other than the study treatment for the changes observed; or
- Death.

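### The adverse-event rule records only what reaches Radiation Oncology, so non-serious contrast reactions seen by other services can go unrecorded

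*Combined protocol and SAP*

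**What the plan says.** Section 4.3 limits the safety record by department: "Only AEs reported to Radiation Oncology discipline per study calendar will be captured and assessed". Section 4.7 repeats the sentence. Section 7.3 applies the same condition to follow-up until resolution, which covers "All subjects experiencing an adverse event that is reported to Radiation Oncology discipline per study calendar".

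The sentence just before the rule in 4.3 makes a wider promise: "Contrast related allergic reactions will also be monitored per CTCAE criteria".

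Section 7.2 gives the timing, "Acute contrast reactions occur within minutes of administration of iodinated contrast", and the rates: "An estimated 3% of patient will experience mild contrast reaction that requires no treatment", while moderate reactions "can occur in about 1 in 250 patients (0.4%) and about 1 in 1600 to 2500 (0.04-0.06%) of patients could experience a severe reaction". It adds that delayed reactions may appear up to 7 days later.

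For renal symptoms, 6.2 tells patients to "report to the treating physician in the event of developing decrease in urine output". The Study Summary describes radiosurgery "as directed by the treating Radiation Oncologist and Neurosurgeon", so that physician could belong to either specialty.

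**The concern.** Whether an event enters the data depends on which department hears of it, and the contrast is given by other departments. Section 1.2 has a neurointerventional specialist working on the angiogram. Section 1.3 says arteriography uses interventional radiology and its recovery area, and that CT angiography needs its own transfer and set-up. Section 4.3 leaves the contrast amount to the radiologists. A reaction that starts within minutes would most naturally be seen first by those teams. No section asks them to pass it on, and no section asks anyone to look in their records.

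At stake is what a low count of contrast reactions could mean. Section 1.2 says CT angiography had not been routine at this institution, partly because of concern about added contrast. Section 4.1 gives it to every subject, and 1.3 suggests it may lower procedural risk. If few or no reactions are recorded under this rule, a reader cannot tell whether few occurred or few were passed on.

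**Working it through.** **Step 1. Which events are exposed to the filter?**

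| Event type | Other route in the protocol | Depends on the departmental filter? |
|---|---|---|
| Serious events and unanticipated problems | 7.4.1: sent to the monitoring committee within 5 business days of study team awareness | Largely not |
| Kidney injury | 4.5, 5.2, 5.3, 6.2: serum creatinine at 1 week and 1 month, with no over-dose condition on that row of the calendar; 9.3: renal toxicity in the interim reports | Largely not |
| Non-serious contrast reactions | None found. Creatinine cannot show them, and the interim reports in 9.3 list renal toxicity only | Yes |

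The gap is in the last row.

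**Step 2. Does the calendar close the gap?** No. The rule applies per study calendar. Footnote 3 in 5.3 makes adverse-event assessment on Day 0, at 1 week and at 1 month conditional on exceeding the recommended contrast dose. Section 7.3.1 then limits follow-up to kidney events in those subjects. A subject within the recommended dose has no scheduled assessment at which a reaction would be asked about. This sits badly with the promise in 4.3 on allergic reactions.

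**Step 3. How many reactions are to be expected?** The plan's own conversions in 7.2 check: 1/250 = 0.4%, 1/2500 = 0.04% and 1/1600 = 0.0625%, printed as 0.06%.

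Inputs: n = 14 (Study Summary, 9.2); mild 0.03, moderate 0.004, severe 0.0004 to 0.0006, midpoint 0.0005 (all 7.2). The rates are per patient, and patients are taken as independent.

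- Any reaction: p = 0.03 + 0.004 + 0.0005 = 0.0345
 - Expected: 14 × 0.0345 = 0.48
 - At least one: 1 − (1 − 0.0345)^14 = 0.39, unchanged to two decimals across the severe range
- Moderate or severe: p = 0.004 + 0.0005 = 0.0045
 - Expected: 14 × 0.0045 = 0.063
 - At least one: 1 − (1 − 0.0045)^14 = 0.061
- Mild share of all reactions: 0.03/0.0345 = 87%

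**Step 4. How many would be lost?** The documents give no capture share, so this is a range under assumption. If a share c of reactions reaches Radiation Oncology, the chance of recording at least one is 1 − (1 − 0.0345c)^14.

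| Assumed c | Expected recorded | Chance of recording at least one |
|---|---|---|
| 25% | 0.12 | 0.11 |
| 50% | 0.24 | 0.22 |
| 75% | 0.36 | 0.31 |
| 100% | 0.48 | 0.39 |

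The primary comparison does not use these data. The 92% power in 9.2 is unaffected.

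**The case against.** The strongest reply is that the rule turns on where an event is reported, not where it is seen. Nothing stops radiology staff or the patient from telling Radiation Oncology, and 7.2 gives the timing of acute reactions but no place. That stands: other services as first observers is an inference from the workflow in 1.2, 1.3 and 4.3. It does not supply a reporting route, and none is written.

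A second reply is that safety is neither an objective nor an endpoint (2.1 to 2.3) and that most reactions would be mild. That is correct and keeps the point modest. The protocol nevertheless commits itself in 4.3 to monitoring allergic reactions.

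Three stronger readings are tempting, and the documents do not support them.

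- *The safety data as a whole are undercounted, and the stopping rule in 7.5 is biased towards no injury.* That rule concerns kidney injury, for which creatinine is scheduled in every subject whoever hears of symptoms. Serious events are reported on study team awareness.
- *Renal symptoms bypass Radiation Oncology because patients call the treating physician.* The Study Summary names the treating Radiation Oncologist alongside the Neurosurgeon, so this is possible but not shown.
- *About one reaction (0.97) should be expected, with a 63% chance of at least one.* This takes 28 administrations: 28 × 0.0345 = 0.97 and 1 − (1 − 0.0345)^28 = 0.63. It treats per-patient rates as per-administration rates and counts the arteriogram, which 1.2 describes as routine care here. Section 7.4 attributes events to the CT angiogram alone.

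**Conclusion.** The point holds for non-serious contrast reactions. As written, 4.3, 4.7 and 7.3 allow such a reaction to be seen by another service and never enter the study record, while 4.3 says allergic reactions will be monitored. About 0.48 reactions are expected in 14 patients, with a 39% chance of at least one and about 6% for a moderate or severe one. These figures assume the rates in 7.2 apply once per patient and that patients are independent. They measure how often reactions occur, not how many would be lost, and the loss cannot be computed from the documents. Undercounting is a structural risk here, not an established result. An amendment is worthwhile because the correction is cheap and a low reaction count would otherwise be uninterpretable.

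**What to change.** In 4.3, 4.7 and 7.3, replace the departmental condition with wording along these lines: contrast reactions and other adverse events within the acute window are captured when known to any study team member or any treating service (radiology, neurointerventional, neurosurgery or radiation oncology), including events noted in the CT and arteriography procedure records. Have the coordinator check those records for each subject.

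In the same amendment, reconcile footnote 3 of the calendar in 5.3, the acute-event and follow-up paragraphs of 7.3.1, and the allergic-reaction sentence in 4.3. If the first two stay as they are, assessment remains limited to subjects above the recommended contrast dose and follow-up to kidney events, which would contradict the new sentence.

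This changes data capture only. It costs the amendment wording and one look at existing procedure notes for each of 14 subjects.
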